# Cognitive behavioral therapy for cocaine addiction to improve antiretroviral medication adherence in HIVpositive patients

# [name]

# A. Study Purpose and Rational

Many research studies have revealed that highly active antiretroviral therapy (HAART) improves HIV-related clinical outcomes, such as decreased opportunistic infections and prolonged survival as well as improves surrogate markers such as HIV viral load and CD4 cell counts [1,2]. Furthermore, optimal adherence to HAART regimens is necessary to obtain adequate viral suppression [3-5] and to avoid the emergence of viral resistance [6]. Patients who are actively abusing illicit drugs, including cocaine, have been shown to demonstrate decreased adherence to HAART as well as inferior virologic and immunologic responses to therapy as compared to both former and non-drug users [7]. Therefore, it is likely that helping these patients eliminate their illicit drug use may improve their adherence to HAART and their HIV clinical outcomes. The purpose of this study is to show that providing active cocaine abusers with cognitive behavioral therapy aimed at relapse prevention and coping skills training will increase their HAART regimen medication adherence as assessed by a self-adherence questionnaire over a 4 month period.

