# B. Study Design and Statistical Analysis

This is a randomized-controlled prospective study designed to assess whether or not a behavioral treatment for cocaine abuse will improve adherence to HAART therapy. The primary outcome of this study is a comparison of adherence to the prescribed HAART regimen in the intervention arm versus the standard of care arm as measured by a standardized three day recall self-assessment questionnaire administered every two weeks throughout the study. The secondary outcomes include viral suppression to undetectable levels using the RT-PCR assay (Roche) of HIV-1 viral load after 4 months and magnitude of change in the log10 viral load from baseline to the 8-week visit. The endpoint of 4 months was chosen, as most individuals who achieve undetectable viral loads will have done so by this time point [1].

Once subjects are identified as cocaine users and express interest in treatment for cocaine abuse, they will be recruited, assessed to see if they fulfill all of the inclusion/exclusion criteria, consented and randomized to either the treatment/intervention arm or the standard of care arm. Randomization will be achieved by selecting an unlabeled sealed envelope from a box containing as many envelopes as potential subjects. Half of the envelopes will say "treatment arm" and half will say "standard of care". In this way, subjects will be randomized.

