Subjects in the standard of care arm of the study will be provided with a list of referrals for substance-abuse treatment including Narcotics Anonymous, individual psychotherapy and rehabilitation programs at the first visit. They will be asked to return once each week for the first 6 weeks of the protocol and then every 2 weeks for the remainder of the study period, which is a total of 4 months. At each of these visits, they will be asked to provide a urine sample that will be tested for cocaine. They will also complete the 3-day adherence questionnaire with one of the investigators every two weeks. These subjects will be provided with additional drug treatment information by the regular clinic social workers and medical practitioners only if they request it according to the current standard of care. At the end of the study, they will be asked which if any of the cocaine treatment resources they utilized. Also, on the last visit, they will complete the Marlowe-Crowne social desirability questionnaire to assess the truthfulness of their self-reported data as compared to the treatment group.

Subjects in the treatment group will have the same number of visits with the same frequency as the standard of care arm, but in addition to providing urine samples every week and completing the adherence questionnaires every two weeks, they will be asked to attend to a 45 minute session at every visit with a trained addiction professional for a session of cognitive behavioral therapy specifically designed to address relapse prevention and coping skills training. Like the standard of care arm, they will be assessed with the Marlowe-Crowne at the last visit and asked about any other addiction treatments they utilized during the study period.

182 subjects will be enrolled in this study, with half participating in each of the two arms. This number will provide enough power to analyze the primary and secondary study outcomes as described below.

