The primary outcome variable is percentage of total prescribed medication doses taken as assessed by a 3 day self-report adherence questionnaire. The percentage of total prescribed doses taken will be compared in the two arms with a  $X^2$  test. Prior studies of non-drug abusers have shown that most patients report approximately a 70-80% adherence rate over the week prior to questioning with a standard deviation of around 20[8]. This self-reported adherence rate correlates with an actual adherence rate of around 55% as measured by microelectronic monitoring systems [8]. In other words, patients usually over report adherence by approximately 15-20% in a reproducible manner that still predicts changes in viral load. There is little data looking at self-reported adherence in a drug abusing population. One study has shown however that 32% of drug users obtain a viral load <400 copies/ml compared to 45% of non-users. The approximately 45% virologic response in non-users in this study is similar to the electronically monitored compliance of 55% in the previous study [7]. The lessened virologic response may be a result of pharmocokinetics and pharmocodynamics as well as viral resistance. Therefore, based on prior studies, non-users of drugs are likely to self-report around 70% adherence. Given, the lack of significant data on active drug abusers, 50% self-reported adherence is a reasonable estimate. To detect this difference, 17 subjects in each group are required.

To detect a  $0.9 \log_{10}$  difference in change in HIV-1 RNA viral load at 8 weeks (the time interval it takes to detect a  $1 \log_{10}$  change in viral load according to national guidelines) between groups assuming a standard deviation of 1.5 by unpaired t-test, a sample size of 45 subjects in each arm is required. Change in viral load is defined as the difference in  $\log_{10}$  copies/ml between the value measured at the time of the initial visit and the value at the 8-week visit. In a study comparing drug users and non-users, a  $0.9 \log_{10}$  difference was detected ( $0.8 \log_{10}$  change in the drug users and a  $1.7 \log_{10}$  change in the non-users) [7].

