#### C. Study Procedure

All subjects participating in the study are to be followed by medical care providers in the outpatient HIV clinic and all medical management will be left to the discretion of those providers. The time intervals chosen in this study for checking viral loads after the initiation of HAART therapy correspond with national treatment guidelines [9]; however additional blood tests are at the discretion of the medical provider. Although it is not possible to blind this study, no data will be shared with either the subjects or their providers. The study period will last 4 months. Study visits will occur once a week for the first 6 weeks and then every 2 weeks thereafter. Subjects in both arms will have a urine dip test to

Columbia University College of Physicians and Surgeons

check for cocaine at every visit which will only take 5 minutes to collect and process. Also, every two weeks the subjects will be asked the questions on the 3-day adherence questionnaire to assess their medication adherence. The questionnaire will take about 15 minutes at these visits. The urine samples and questionnaires will be completed with an investigator in the HIV outpatient clinic prior to any medical visit that subject might have that day. The subjects in the treatment arm will have therapy sessions in the addiction medicine research clinic on the same days as their other study activities. All subjects will receive compensation for coming to the scheduled visits and providing urine samples in the form of vouchers. They will receive a \$15 voucher at each visit in the form of subway fare (Metrocard) or a voucher to a local fast food chain. If they complete the study and come to all of the scheduled visits, they will receive a \$50 gift certificate to Old Navy.

At the first visit, informed consent will be obtained and the study will be explained to the patient by one of the investigators. Also, the primary medical provider will initiate HAART therapy. Because adherence to the prescribed regimen is the primary outcome, patients may be placed on any of the "strongly recommended" regimens according to current national guidelines [9] at the discretion of the primary medical provider as long is the regimen is a class sparing regimen. (e.g. NNRTI-sparing, PIsparing or a PI- and NNRTI-sparing regimen) The medical care provider will choose a regimen at the first study visit while still blinded to which arm of the study the patient is in to avoid biasing the choice.

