# G. Study Subjects

In order to be included in this study, the patient must meet the following inclusion criteria:

- 1) Have documentation of HIV-1 positive status
- 2) Have a positive score on the Drug Abuse Screening Test (DAST)
- 3) Use cocaine regularly and more often than any other drug or alcohol
- 4) Express an interest in stopping their cocaine use
- 5) Must not be currently taking antiretroviral therapy
- 6) Have a viral load >55,000 copies/ml and a CD4 count < 200; thereby placing the subject in a category that should definitely receive therapy according to national guidelines [8b]. Treatment at higher CD4 loads and lower viral loads has still not been shown to affect clinical outcomes of time to disease progression and given the likelihood of non-adherence in drug-abusing populations is higher than in the general population, it may be unethical to start people on HAART when there are uncertain recommendations at present.

If a subject meets any of the following exclusion criteria, they will not be allowed to participate in the study:

- 1) On any form of antiretroviral therapy within the 4 months prior to the study
- 2) Exhibiting signs of physical dependence on any drug other than cocaine
- 3) Living in a facility where medicines are dispensed for them
- 4) Unable to give informed consent

Subject participation will not be limited on the basis of gender or race. Based on population of the community in which the study is to take place, Caucasian, Latino and African-American subjects will be primarily recruited. It is likely that slightly more men will be included in men as there are a larger proportion of male drug abusers in the general population.

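### Never-treated and previously treated subjects enter together, but the two viral-load comparisons ignore prior exposure: a small, cheaply recovered loss of precision

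*Protocol*

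**What the plan says.** Two eligibility rules in Protocol section G deal with earlier treatment. Inclusion criterion 5 reads "Must not be currently taking antiretroviral therapy". Exclusion criterion 1 removes anyone "On any form of antiretroviral therapy within the 4 months prior to the study". Neither requires a subject to be treatment-naive.

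Section C then handles all subjects alike at the first visit: "Also, the primary medical provider will initiate HAART therapy". Viral-load timing is counted from that start: "The time intervals chosen in this study for checking viral loads after the initiation of HAART therapy correspond with national treatment guidelines".

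Allocation (section B) has no strata: "Randomization will be achieved by selecting an unlabeled sealed envelope from a box containing as many envelopes as potential subjects". On size, the same section says "182 subjects will be enrolled in this study, with half participating in each of the two arms".

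Section B names the tests for the two secondary viral-load outcomes. The 8-week change in log10 viral load is compared by an unpaired t-test, and the proportion undetectable at 16 weeks by a chi-square test. Neither is adjusted. A multiple linear regression is also planned, but its outcome is adherence. Its variable list does not name prior antiretroviral exposure, although it ends with an open clause.

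On resistance, section A says good adherence is needed "to avoid the emergence of viral resistance". Section B says of drug users: "The lessened virologic response may be a result of pharmocokinetics and pharmocodynamics as well as viral resistance".

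**The concern.** A subject who has never taken antiretrovirals and one who stopped a failing regimen five months ago can both enter, and both are analysed as starting therapy. A washout clears the drug but not the treatment history. By the protocol's own account, resistance is tied to poor adherence and may weaken virologic response. Prior exposure is therefore a plausible baseline predictor of both viral-load outcomes.

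An unadjusted comparison leaves the variation due to such a predictor in the error term. If the arms happen to differ in their share of previously treated subjects, the estimated difference moves with that imbalance. The 16-week comparison is the one to watch, because it sets the total of 182 and has the least spare power. Adjustment is possible later only if the variable has been collected, and the protocol does not describe collecting it.

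**Working it through.** **Inputs from Protocol section B.** 91 per arm; suppression 40% v 20%; week-8 difference 0.9 log10 with SD 1.5, for which 45 per arm are stated.

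**Assumptions, not in the documents.** Two-sided alpha 0.05 and 80% power (neither is stated; they reproduce the stated sizes). Share previously treated, q, from 20% to 50%. Gap between never-treated and previously treated subjects, g, of 10 to 20 points in suppression and 0.3 to 1.0 log10 in week-8 change.

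**1. The plan's own figures.**
- Suppression: n = [1.96·√(2·0.3·0.7) + 0.842·√(0.4·0.6 + 0.2·0.8)]² / 0.2² = 81.2. With continuity correction, (81.2/4)·[1 + √(1 + 4/(81.2·0.2))]² = 90.9, so 91 as stated.
- Week-8 change: n = 2·(1.96 + 0.842)²·1.5²/0.9² = 43.6. The exact t-test gives 44.6, so 45 as stated.

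**2. Chance imbalance in the share previously treated.** The standard error of the between-arm difference in share is √(2q(1−q)/91).

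| q | SE | 95% limit | Chance of more than 10 points |
|---|---|---|---|
| 20% | 5.9 points | ±11.6 points | 9% |
| 30% | 6.8 points | ±13.3 points | 14% |
| 50% | 7.4 points | ±14.5 points | 18% |

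**3. Shift in the result at the 95% limit.** Shift = limit × g.
- Suppression: from 0.116 × 10 = 1.2 points to 0.145 × 20 = 2.9 points, against a planned 20.
- Week-8 change: from 0.116 × 0.3 = 0.035 to 0.145 × 1.0 = 0.145 log10, against a planned 0.9.

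For scale, the standard error of the suppression difference is √((0.24 + 0.16)/91) = 6.6 points, so the largest of these shifts is under half a standard error.

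**4. Precision, suppression.** Unadjusted power at 91 per arm without continuity correction is Φ[(0.20 − 1.96·√(0.42/91))/√(0.40/91)] = Φ[(0.20 − 1.96·0.0679)/0.0663] = 84.3%. The stratified analysis holds the overall rates at 40% and 20% and uses within-stratum variances:
- q = 20%, g = 10 points: control rates 22% and 12%, treatment rates 42% and 32% (never-treated, previously treated). Power = Φ[(0.20 − 1.96·0.0677)/0.0660] = 84.6%.
- q = 50%, g = 20 points: control rates 30% and 10%, treatment rates 50% and 30%. Power = Φ[(0.20 − 1.96·0.0663)/0.0646] = 86.1%.

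The gain is 0.3 to 1.8 points.

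**5. Precision, week-8 change.** If 1.5 is the SD within each group, the total SD is √(1.5² + q(1−q)g²), at most √(2.25 + 0.25) = 1.58. The size needed is then at most 2·(1.96 + 0.842)²·2.5/0.81 = 48.4, so 49 per arm, and power at 91 per arm stays at about 97% or more. If 1.5 is instead the total SD, adjustment lowers it to √(2.25 − 0.25) = 1.41 at best, and the size needed falls from 44 to 39 (normal approximation).

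**The case against.** The strongest reply is that the choice of covariates is commonly left to a statistical analysis plan, which is not shown here, and that the effect is trivial. Much of this stands. Randomisation protects the comparison, because treatment history precedes allocation. Section C also has the provider choose the regimen before knowing the arm. Chance imbalance is already within the variance of the unadjusted tests, so type I error is not affected. The planned 91 per arm need not rise for noise alone.

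Two things are left. The protocol does state its tests, and the stated ones are slightly less efficient than an available alternative. And a later analysis plan cannot adjust for a variable that was not collected.

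Four stronger readings are tempting, and the documents do not support them:
- *The viral-load results are biased.* They are not; this is a matter of precision and chance imbalance.
- *The primary adherence comparison is affected too.* Nothing in the protocol shows that prior exposure predicts adherence, and the open clause in the adherence regression could take it in anyway.
- *The protocol asserts that resistance lowers response in previously treated subjects.* Section B says only that resistance may contribute, among other causes, when comparing drug users with non-users. It does not mention prior treatment.
- *The therapy works less well in previously treated subjects, so power is badly overstated.* If 30% were previously treated and had half the effect, the rates would be 20% + 20%·(1 − 0.3·0.5) = 37% v 20%, and power would be about 72%. The documents give no data for such a difference, and adjustment would not restore the loss.

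It is also fair to say that a never/previously treated flag is only a proxy for resistance, so the gains above depend on how well it separates outcomes.

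**Conclusion.** The point holds as a modest improvement to the two secondary viral-load analyses. The eligibility rules admit a mixed population, the protocol itself gives a reason why treatment history could matter for virologic response, and neither the randomisation nor the stated viral-load tests use it. Exclusion criterion 1 is not wrong, and no stated sample size is in error.

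The size is small: about 0.3 to 2 points of power for suppression, and shifts at the 95% imbalance limit that are well below the planned effects. These figures rest on the assumed share (20-50%) and gaps (10-20 points; 0.3-1.0 log10). If few subjects were previously treated, or their outcomes hardly differed, the gain would be close to nil.

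**What to change.** Keep exclusion criterion 1. Record prior antiretroviral exposure at baseline, before allocation, as never or stopped at least 4 months ago. In section B, prespecify it as a covariate in the comparison of week-8 log10 change (a linear model in place of the t-test) and as the stratum in a Mantel-Haenszel test of 16-week suppression (in place of the plain chi-square test). A supportive analysis of both outcomes in treatment-naive subjects is optional.

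The cost is one baseline field and slightly more analysis work. The field needs a lifetime treatment history, which is somewhat more than the 4-month history that exclusion criterion 1 strictly requires. Eligibility, treatment and sample size do not change.

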#### H. Recruitment of Subjects

Subjects will be recruited at New York Presbyterian Hospital's Columbia Presbyterian Medical Center over a two-year period in both the outpatient HIV clinic as well as in the inpatient setting. All patients who present to the HIV clinic or the inpatient service for treatment of HIV or HIV-related diseases will be screened with the Drug Abuse Screening Test (DAST). If it is positive, the patient would like help with their drug abuse and the patient's primary drug of abuse is cocaine, they will be recruited to participate in the study.

# I. Confidentiality of Study Data

None of the data being collected during the study will be shared with the medical providers, the subjects or anyone else other than the primary investigators. Each subject will be assigned a unique identifier code number to identify his or her data (lab tests, drug tests, questionnaire data). This number will have no relationship to the arm of the study the subject is participating in. Hence, the support staff performing urine drug tests, serologic tests (viral loads and CD4 counts) and administering the adherence questionnaires will be blinded to which arm of the study the patient is participating in. All data will be stored in a secure database accessible only to the investigative team.

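### Sections C and I bar giving any study data to treating providers, with no clinical exception; if the week-8 and week-16 viral loads are study-run tests, guideline-timed results are withheld

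*Protocol*

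**What the plan says.** Two sections of the protocol restrict disclosure.

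- Section I, on confidentiality, opens with this rule: "None of the data being collected during the study will be shared with the medical providers, the subjects or anyone else", with only the primary investigators excepted. The same section assigns each subject a code number "to identify his or her data (lab tests, drug tests, questionnaire data", so lab tests count as data. It then lists, among staff to be kept blind to arm, "the support staff performing urine drug tests, serologic tests (viral loads and CD4 counts".
- Section C (Study Procedure): "Although it is not possible to blind this study, no data will be shared with either the subjects or their providers".

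Neither section makes an exception for results needed in clinical care, and no other section supplies one.

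Section C also describes the treating provider's role: "the primary medical provider will initiate HAART therapy" at the first visit, and "all medical management will be left to the discretion of those providers". On test timing it says "The time intervals chosen in this study for checking viral loads after the initiation of HAART therapy correspond with national treatment guidelines", and then that "additional blood tests are at the discretion of the medical provider". Section E describes the Roche viral load assay as the one that guidelines recommend for steering treatment. Section B makes the viral load change at 8 weeks and suppression at 16 weeks the secondary outcomes. Section G requires an entry viral load above 55,000 copies/ml and a CD4 count below 200.

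**The concern.** The protocol times a treatment-guiding test to national guidelines and leaves treatment to the clinic provider, then forbids passing on study data, a term it defines to include lab tests. Patients enter with advanced disease and start a new regimen on the day they join. The viral load at 8 weeks is what shows whether that regimen is working.

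If the study runs these tests and staff follow the rule as worded, the provider lacks the week-8 and week-16 results or must order the same test again. The stake is patient care rather than the validity of the analysis, and it depends on who runs the tests.

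**Working it through.** No figure in the protocol bears on the rule itself, so the first two steps compare texts. Steps 3 to 5 size the rule's reach and the cost of changing it.

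**1. Does the rule reach viral load and CD4?** Yes. Section I lists lab tests as subject data and names both assays. Viral load is also a secondary outcome in Section B, so it is data collected during the study. The protocol gives no follow-up schedule for CD4, so the guideline-timing argument applies to viral load only.

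**2. Who runs the week-8 and week-16 tests?**

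| Pointing to study tests | Pointing to clinic tests |
|---|---|
| Section C speaks of intervals chosen in this study, and calls the provider's own tests additional | The visit procedures in Sections B and C list urine samples and questionnaires but no blood draw |
| Section I has blinded support staff performing viral loads | Section C leaves medical management to the clinic provider |

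The left column is the stronger but does not prove the point. The consequences differ:

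- Study tests: following the rule withholds the result or leads to duplicate testing.
- Clinic tests: the provider holds the result already. The study has not shared it, so the rule is kept and nothing is lost clinically.

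**3. Reach, if they are study tests.** With 182 subjects and full retention: 182 at week 8 + 182 at week 16 = 364 results at most.

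**4. Cost of release for adherence (primary outcome).** Assume questionnaires every two weeks from week 2 to week 16, which gives 8. Those after week 8 (weeks 10, 12, 14, 16) number 4. The planned difference in Section B is 70% − 50% = 20 points. As a deliberately severe case, let it vanish entirely after week 8. With equal weights:

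(4 × 20 + 4 × 0)/8 = 10 points.

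SE = SD × √(2/91); power = Φ(10/SE − 1.96), two-sided 5% (assumed), no dropout.

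| SD | SE | Power for 10 points |
|---|---|---|
| 20 (Section B) | 2.965 | 92% |
| 25 (assumed) | 3.706 | 77% |
| 30 (assumed) | 4.447 | 61% |

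This is a comparison of means. Section B names a χ² test for adherence, so these figures are illustrative and are not the power of the planned test.

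**5. Cost of release for week-16 suppression.** Section B plans 91 per arm for 40% against 20%. Two-proportion z test, two-sided 5%, where p̄ is the mean of the two proportions:

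power = Φ{[Δ − 1.96 √(2p̄(1−p̄)/91)] / √([p₁(1−p₁) + p₂(1−p₂)]/91)}.

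For 40% against 20%: Δ = 0.20, p̄ = 0.30, giving (0.20 − 1.96 × 0.0679)/0.0663 = 1.008, so power is 84%. With a continuity correction it is 80%, which is consistent with the protocol's 91 per arm. If release raised suppression in the standard-of-care arm alone by an assumed 1 to 3 points:

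| Standard of care | Power | With continuity correction |
|---|---|---|
| 20% | 84% | 80% |
| 21% | 80% | 75% |
| 22% | 75% | 70% |
| 23% | 70% | 64% |

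The week-8 viral load change is measured before anyone could act on its result, so release does not touch it.

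**The case against.** The strongest reply is that the rule was never meant for clinical results. In Section C it follows directly from the admission that the trial cannot be blinded, so it reads as a substitute for blinding. Much of the Section I paragraph concerns coding and keeping test staff blind. Treatment starts on the strength of entry viral load and CD4 values, so a ban covering such values would sit oddly with the protocol's own treatment pathway. This is plausible as to intent. But neither section limits the rule that way, Section I states it without the blinding context, and staff follow the wording.

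Second, providers may order their own blood tests. That stands: they are not cut off, and it limits the harm. It works by repeating a test, however, and is not an exception to the rule.

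Two stronger readings are tempting and are not supported. A reader might infer that results will in fact be withheld; the protocol does not establish this, because it does not settle who runs the tests. A reader might also infer that the rule cannot be followed if these are clinic tests. It can: the rule limits what the study hands out, and clinic results can enter the study database with nothing flowing back.

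A last objection is that Part B of the adherence questionnaire asks about side effects, feeling ill and depression, which would stay withheld under the change proposed here. That is true, but patients can report these to their provider directly. They cannot report a viral load they have not been given.

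**Conclusion.** The concern holds conditionally. As worded, Sections C and I bar all study data, lab tests included, from treating providers and subjects without a clinical exception. If the week-8 and week-16 viral loads are study tests, as the wording suggests without settling, compliance withholds up to 364 guideline-timed results or forces duplicate testing. If they are clinic tests, there is no clinical consequence. The protocol gives no basis for counting how many results would change care.

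This is worth correcting because the rule is stated outright and the correction is cheap. It is not evidence that patients would be harmed. The power figures describe only the price of the correction and rest on the assumptions shown with them. If these are clinic tests, release changes nothing and that price is zero.

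**What to change.** In both Section C and Section I:

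1. Limit non-disclosure to urine cocaine results and the adherence and social desirability questionnaires.
2. Keep the existing provision in Section C that the provider chooses the regimen while blind to arm. Do not list arm as withheld from subjects; those attending therapy sessions necessarily know it.
3. State that viral load and any CD4 results go to the treating provider on the same schedule in both arms. Saying whether the study or the clinic runs the week-8 and week-16 tests would remove the ambiguity.

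The cost is a few sentences of text and some possible dilution. A provider who sees a poor week-8 result may act on it, and if that happens more often in the arm responding less well, the arms may draw together slightly. That would reflect usual care. Adherence has room for this at the SD of 20 given in Section B, and less at larger SDs. Week-16 suppression has little slack, since the sample size was set by that comparison. Releasing on one schedule in both arms keeps the information given to providers the same across arms.
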